## G. Description of monitoring activities

### a) Monitoring

Monitoring visits will be conducted during the enrolment, follow-up and close out study phases in accordance with Symbios / TRIUM SOPs and the Monitoring Plan. The purpose of monitoring of the study is to verify compliance with the clinical protocol, the EU Regulation and ISO 14155. It will be conducted by an independent qualified monitor or CRA (TRIUM, external partner or CRO). Monitoring oversight will be provided by Symbios. 100% of the Informed Consents will be reviewed for accurate completion.

eCRF data related to the primary and secondary endpoints as well as study-specific adverse events will be verified against the patient’s medical records.

 10.1080/17453674.2019.1599252 (Evaluation of Forgotten Joint Score in total hip arthroplasty with Oxford Hip Score as reference standard)

SYMBIOS		 symbios  Clinical Investigation Plan	F029.03
Date	27.11.2019		Distribution Informatique pdf
Auteur	BGA		
Contrôle	EBO		
Libération	RAQ		

Site personnel will complete e-CRFs following each subject visit. Study data submitted will be reviewed against patient files and sources containing original records of patient data. Source document verification will occur in accordance with the Monitoring Plan.

The progress of the study will be monitored by:

- On-site review, as deemed appropriate by TRIUM CRA
- Telephone communications between the site personnel (e.g., investigator, study coordinator) and study monitor
- Review of e-CRFs and the associated clinical records
- Review of regulatory documents
- Review of ISF content

The Principal Investigator will permit direct access to study monitors and appropriate regulatory authorities to the study data, to the corresponding source documentations in order to verify the accuracy of these data.

#### *b) Accessibility of investigation site staff and study materials*

The principal investigator(s), his/her delegate(s) and the study coordinator(s) shall be accessible to Symbios Clinical Study Manager and/or to the monitor or to Symbios representative. This accessibility is of particular importance for reviewing data in the electronic Case Report Form (CRF). Direct access to patient medical files for source data verification will need to be granted and prepared prior to any monitoring visits.

#### *c) Audits and investigation site inspections*

In addition to regular monitoring visits, Symbios may conduct audits at participating investigation site. The purpose of an audit is to verify the adequate performance of the clinical study related activities. Regulatory bodies may also perform inspections at participating investigation site. Any regulatory authority inspection announcements shall be forwarded immediately to the Clinical Affairs Manager. The investigator and/or institution shall permit Symbios and regulatory bodies direct access to source data and documents, taking into account any restrictions due to local law, to perform clinical study-related monitoring, audits, EC review, and regulatory inspections.

## **H. Factors that might compromise study interpretation of results**

Anticipated factors that could compromise study interpretation of data and a lack overview of clinical data:

- Differences in patient selection that may not be easily documented, which could lead to differences in outcome that are mistakenly attributed to the use of the new device such as ORIGIN
- Higher loss of study population (higher than >10% expected)
- Low quality of data collection (if not study monitoring oversight)

SYMBIOS		 symbios  Clinical Investigation Plan	F029.03
Date	27.11.2019		Distribution Informatique pdf
Auteur	BGA		
Contrôle	EBO		
Libération	RAQ		

- Traceability and consistency of collected data
- Statistical differences could be in baseline demographics between ORIGIN vs VANGUARD in patient satisfaction, including slightly differences in age, comorbidities and sex.
- Surgeon overall satisfaction regarding both implants ORIGIN and VANGUARD and possible surgical factors who could play a role in the patient outcome or on the performance of the implant
- Heterogeneity in subjects regarding their answers in the FJS self-questionnaire

The choice of investing in a long-term EDC solution to collect and store the data will leverage the full potential of Symbios clinical data in order to mitigate the factors that might compromise study data interpretation and analysis.

SYMBIOS		 symbios  Clinical Investigation Plan	F029.03
Date	27.11.2019		Distribution Informatique pdf
Auteur	BGA		
Contrôle	EBO		
Libération	RAQ		

## IX. MONITORING PLAN

---

The Monitoring Plan defines the extent and type of the monitoring activities, describes the responsibilities of those involved as well as trial specific aspects and include the Symbios / TRIUM SOPs governing monitoring activities.

Cf. CHAPTER XXI. APPENDICES. MONITORING PLAN.

SYMBIOS		 symbios  Clinical Investigation Plan	F029.03
Date	27.11.2019		Distribution Informatique pdf
Auteur	BGA		
Contrôle	EBO		
Libération	RAQ		

## X. STATISTICAL ANALYSIS

---

### a) *Sample size*

The size of the two groups depends on several factors which are involved in the hypothesis made (see table 1).

P value is the probability.

*Table 1*

Table of Error types		HO is	
		TRUE	FALSE
Decision about HO	Don't Reject	Correct, True negative: $p=1-\alpha$	False negative: $p=\beta$ type II Error
	Reject	false positive: $p= \alpha$ type I Error	Correct, true positive: $p=1- \beta$

### Statistical Risk

The standard practice in clinical studies is to set:

- $\alpha = 0.05$  (5%), this will give us an Interval of confidence of 95%
- $\beta = 0.2$  (20%), this will give a power of 80%

### Statistical Parameters

In addition to the risk  $\alpha$  and  $\beta$ , the Effect Size (ES) must as well as the variance ( $\sigma^2$ ) must be known and set.

The ES is the effect product by the difference of treatment between the two groups, in this case it is the MCID calculated previously in section V.A divided by  $\sigma$  (standard deviation).

- ES:  $ES = \frac{\mu_1 - \mu_2}{\sigma}$
- $\sigma^2$ :  $\sigma^2 = \frac{1}{n} \cdot \sum_{i=1}^n (y_i - \mu)^2$  (with  $\mu$ , average of population, and  $x_i$  a single value)
- 

### Hypothesis considered

Considering following hypothesis:

- Provided that the studied responses ( $Y_1$  and  $Y_2$ ) are independent variables
- Provided that group size will be larger than 30, so that by the Central Limit Theorem (CLT) can be applied ( $Y_1$  and  $Y_2$  normally distributed, Gaussian)
- Provided that the patients ( $x_{ij}$ ) are randomized
- Provided that  $\sigma$  is equivalent within the two group ( $\sigma_1 = \sigma_2$ )

### Calculation

According to the hypothesis considered, the Z distribution can be used to figure the group size ( $n$ ):

SYMBIOS		 symbios  Clinical Investigation Plan	F029.03
Date	27.11.2019		Distribution Informatique pdf
Auteur	BGA		
Contrôle	EBO		
Libération	RAQ		

$n: \quad n = 2/ES^2 \cdot (z_{1-\alpha/2} + z_{1-\beta})^2$

- $ES = MDIC / \sigma \quad 13.4/26.8=0.5$
- $Z_{1-\alpha/2}=1.96$
- $Z_{1-\beta}=0.84$

⇒  $n \geq 63$  per group.

#### Lost patient

Typically, the margin of lost patient is within 10% which in our case is rounded to 7 patients per group.

#### Final figures for group's size

$n_1 = 70$  patients

$n_2 = 70$  patients

#### *b) Patient Reported Outcomes Measures (PROMs)*

The Minimal Clinical Important Difference (MCID) is the minimum difference in Patient Reported Outcomes Measures (PROM) that is meaningful for the patient.

With a distribution-based approach, the ability of patient to discriminate each task after the surgery is approximately half a Standard Deviation. Therefore, for the purpose of this study, MCID will be evaluated by half of the Standard Deviation (SD) of the Forgotten Joint Score. (cf. Primary endpoints)

A literature review on the FJS in TKR has been performed (cf. Chapter XX: Bibliography). Literature shows that the SD of the FJS can be evaluated at 26.8 points.

For the purpose of this study, half of the SD is set at 13.4 points for patient satisfaction between Origin versus VANGUARD.

#### *c) Analysis of clinical data and Safety outcomes*

The rate of serious adverse events (SAE) and Unanticipated Adverse Device Effects (UADEs) during the study will be presented using the proportions of patients experiencing one or more of each SAE and UADE. All serious and non-serious adverse events will be characterized in terms of severity and relatedness to the operative procedure and device. Additionally, the percent of patients requiring one or more secondary surgical procedures relating to the original procedure will be presented. Data will be analyzed for all patients enrolled in this observational study.

#### *d) Performance outcomes*

The device success will be evaluated via the performance assessment via the overall surgeon and patient satisfaction. Post-operative surgeon overall satisfaction will be assessed via the following answers: very

 <https://www.ncbi.nlm.nih.gov/pubmed/12719681>

Interpretation of changes in health-related quality of life: the remarkable universality of half a standard deviation

SYMBIOS		 symbios  Clinical Investigation Plan	F029.03
Date	27.11.2019		Distribution Informatique pdf
Auteur	BGA		
Contrôle	EBO		
Libération	RAQ		

satisfied, satisfied, and not satisfied. Post-operative patient satisfaction will be assessed via the FJS, with a marked improvement in the natural feel of the prosthesis during the first year after the surgery, and slightly significant improvement at the following interval of 2 years.

A final report will be prepared when all patients have completed their follow-up evaluation. No interim analysis is planned.

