### B. Clinical endpoints

#### a) *Primary endpoints*

- The hypothesis regarding the scoring is that patients receiving ORIGIN implants will experience a more natural feel of the prosthesis during the first year after the surgery compared to patients receiving VANGUARD implants (as measured with FJS)
- The primary endpoint of this study is:

SYMBIOS		 symbios  Clinical Investigation Plan	F029.03
Date	27.11.2019		Distribution Informatique pdf
Auteur	BGA		
Contrôle	EBO		
Libération	RAQ		

- To compare the ability of patients to forget their operated knee at 1 year after the surgery, measured by the Forgotten Joint Score 12 (FJS-12 Knee).
- To compare patient satisfaction regarding the surgery with a CE marked custom-made implant (ORIGIN®) versus off-the-shelf (VANGUARD PS) device. A short self-reported questionnaire will be used.

*b) Secondary endpoints will evaluate clinical performance and safety of ORIGIN System:*

- **Secondary endpoints:**

- Evaluate the success of the procedure
- Evaluate surgeon satisfaction regarding the use of implants and instruments
- Evaluate outcomes: complications & revision rate with the ORIGIN SYSTEM at the last (2y) follow-up visit
- To compare the PROMs between the two groups at 1y follow-up and 2y follow-up visits.
- Evaluate performance of the ORIGIN System vs VANGUARD PS at 2 years follow-up: clinical examination and scoring.
- To evaluate/compare the clinical, functional and quality of life outcomes using the following four scores:
  - Clinical examination
  - The Knee Injury and Osteoarthritis Outcome Score (KOOS)
  - The Oxford Knee Score (OKS)
  - The EQ-5D-5L Score
  - A self-administrated patient satisfaction questionnaire.
- To evaluate/compare the clinical, functional and quality of life outcomes with the following surgeon reported scores:
  - The Knee Society Score (KSS) (Objective Knee Indicators only)
  - Knee Society Radiographic Evaluation and Scoring System (KSRESS)
  - The Single Leg Stance Test (SLS)
  - The Timed Up & Go test (TUG)
- Radiological evaluation:
  - X-rays: AP, lateral, sunrise, long leg weight bearing film
  - Femoral patellar arthrosis: Iwano classification (stage 1 mild to 4 very severe),
  - KRESS Radiological assessment: Patellar tilt angle, patellar displacement, tibial slope, anatomical axis (angles  $\alpha - \beta$ ), mechanical axis, (HKA angle, F angle, T angle, HKS angle)

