## 2. Attempted procedure

An attempted procedure is one where:

- The patient has been randomized to ORIGIN arm but won't receive the prosthesis (neither the VANGUARD) because the 3D preoperative planning of the design has shown shape incompatibilities or abnormalities.
- The study subject has entered the procedure room for implantation but did not receive an ORIGIN implant for any reason. (Implants broken or defective, use of another implant VANGUARD excluded in that case)

If a procedure was attempted, and the ORIGIN is not implanted, the subject will be followed for safety reporting for 30 days post-attempted implant, and then exited from the study. Adverse Events data should be collected on the AE e-CRF.

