### e) *Statistical Methods and Analysis*

All analyses will be described in a Statistical Analysis Plan (SAP) which will be completed prior to analysis. No interim analysis is planned.

Any deviations from this section and/or the Statistical Analysis Plan will be described and justified in the Final Clinical Study Report, as appropriate.

No statistical techniques will be used to impute missing data for continuous or categorical outcomes. If a subject's data are missing for any reason, that subject will not be included in that portion of the analysis. The number of subjects included in each analysis will be reported so that the reader can assess the potential impact of missing data.

Additional (annual) reports providing only descriptive statistics will only be written upon request of the EC/IRB and/or Regulatory Authority, as applicable.

For statistical analysis, patient satisfaction results will be analyzed into the knee awareness as:

- Never
- Almost never
- Seldom
- Sometimes
- Mostly

The subjects that required further procedures or surgeries on their knee in the initial six months were excluded from this analysis. These patients were excluded from analysis because the outcome and satisfaction scores were likely to be highly influenced by the early additional procedure, and the study was not powered to evaluate the revision rates associated with two implants.

Statistical differences could be identified in:

- Baseline demographics between ORIGIN vs VANGUARD in patient satisfaction, including slightly differences in age, comorbidities and sex.
- Surgeon overall satisfaction regarding both implants ORIGIN and VANGUARD and possible surgical factors who could play a role in the patient outcome or on the performance of the implant?
- Demonstrate superiority of ORIGIN over VANGUARD: higher score by 13.4 points based on MCID evaluation of PROMs.
- If a modular stem is used it could impact radiological analysis: radiolucencies for instance and tibial loosening

SYMBIOS		 symbios  Clinical Investigation Plan	F029.03
Date	27.11.2019		Distribution Informatique pdf
Auteur	BGA		
Contrôle	EBO		
Libération	RAQ		

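### Device success is judged by surgeon and patient satisfaction, and the plan's own rules drop never-implanted and early re-operated patients from the patient part, so those failures cannot count there

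*Combined protocol and SAP*

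**What the plan says.** Among the secondary endpoints, the synopsis and VI.B list "Evaluate the success of the procedure" without defining it. The only text on how success is judged is X.d: "The device success will be evaluated via the performance assessment via the overall surgeon and patient satisfaction". For the patient half it adds: "Post-operative patient satisfaction will be assessed via the FJS". The surgeon half is a three-level rating in X.d. The form shown in VIII.F.1 is a two-level one, written for ORIGIN and completed during surgery.

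Three rules elsewhere decide who can contribute to the patient half:

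- **VIII.F.2 (attempted procedure).** This covers an ORIGIN patient whose 3D planning shows an incompatible shape. It also covers this case: "The study subject has entered the procedure room for implantation but did not receive an ORIGIN implant for any reason", with a broken or defective implant among the examples. For such a patient, "the subject will be followed for safety reporting for 30 days post-attempted implant, and then exited from the study".
- **X.e (missing data).** Nothing is imputed, and where data are missing, "that subject will not be included in that portion of the analysis".
- **X.e (early re-operation).** "The subjects that required further procedures or surgeries on their knee in the initial six months were excluded from this analysis", because "the outcome and satisfaction scores were likely to be highly influenced by the early additional procedure".

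Separately, X.c reports serious adverse events, unanticipated device effects and the percentage of patients with related secondary surgery, for all enrolled patients. VI.B lists complications and revision rate as another secondary endpoint. VII.H says that early discontinuers are analysed where appropriate.

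**The concern.** A success endpoint should fall when the device cannot be implanted or when the knee needs early re-operation. Here both events take the patient out of the patient half of the measure. The reason given in X.e for the six-month exclusion, that early surgery affects the scores, argues against using it for this endpoint, because that effect is what a success measure is meant to register. The exclusion also depends on an event after randomisation.

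The attempted-procedure rule is written for ORIGIN only, and only ORIGIN has CT-based planning and a patient-specific implant (VII.D). One arm therefore has a removal route that the other lacks, in a study whose results are meant to support the sponsor's Clinical Evaluation Report (IV.D).

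**Working it through.** **1. The rules side by side.**

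| Event | Patient half (FJS) | Surgeon half | Safety reporting |
|---|---|---|---|
| ORIGIN planning failure, no surgery | Exited after 30 days (VIII.F.2), so no 1- or 2-year FJS; dropped as missing (X.e) | No operation, so no form | Adverse events collected for 30 days; the failure itself need not be an adverse event |
| ORIGIN not implanted, patient in the procedure room | Same as above | A form may exist; no rule excludes it | Adverse events collected for 30 days |
| Further knee procedure within six months, either arm | Excluded (X.e) | A rating from the first operation may exist; a form filled in during surgery does not clearly capture a later event | Counted in X.c if related to the original procedure |
| Further knee procedure after six months | Stays in | As above | Counted in X.c if related to the original procedure |

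The scope of the six-month exclusion is not spelled out. It directly follows the sentence on analysing patient satisfaction as knee awareness, and its stated reason concerns satisfaction scores, so it reaches the FJS-based half of success.

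**2. The plan's own figures.** X.a gives n = 2/0.5² × (1.96 + 0.84)² = 8 × 7.84 = 62.7, so 63 per group, plus 7 for loss = 70. This reproduces and is not in dispute. X.d states no success rate or threshold, so there is no success figure to reproduce.

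**3. Illustration of size.** Inputs:

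- 70 patients per arm and 7 lost (X.a), which leaves 63.
- 96% satisfied or very satisfied (IV.B). This comes from the sponsor's separate post-market study and stands in for a success rate that X.d does not define.
- a attempted procedures and r early re-operations. These counts are assumed, because the documents give neither rate.

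Analysed = 63 − a − r. Successes = 0.96 × analysed. Rate with failures counted = successes / 63.

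| a, r | Analysed | Successes | With removals | With failures counted |
|---|---|---|---|---|
| 1, 1 | 61 | 58.56 | 96.0% | 93.0% |
| 2, 1 | 60 | 57.60 | 96.0% | 91.4% |
| 3, 2 | 58 | 55.68 | 96.0% | 88.4% |

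**4. Are such counts plausible?** IV.B reports revision in 0.25% at a mean of 1.0 year (399 procedures) and in 5.3% at a mean of 0.6 year (19 registry knees). In 70 patients that is 70 × 0.0025 = 0.2 to 70 × 0.053 = 3.7 revisions. These are revision rates, not rates of any further procedure within six months, and the upper one is about one event. They show that small counts are possible and do not fix a value. For attempted procedures the documents give nothing.

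**The case against.** **The failures are reported elsewhere.** This stands for re-operations and revisions: X.c counts related secondary surgery in all enrolled patients, VI.B lists revision rate, and X.e requires the number analysed to be shown. A reader might infer that these events vanish from the results; they do not. But safety reporting does not correct a success measure computed without those patients, and a planning failure need not appear under X.c at all.

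**The surgeon half has no exclusion.** This also stands. A reader might infer that these failures cannot count anywhere in device success. That goes too far: a defective implant found in the procedure room could be rated as not satisfactory. Only the planning failure clearly escapes both halves. X.d also does not say that satisfaction is the sole criterion; that is inferred because no other is given.

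**The direction is not established.** A reader might infer a net bias towards ORIGIN. The six-month exclusion applies to both arms and its net direction is unknown. Only the planning route is specific to ORIGIN, and its frequency is unknown.

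**The percentages have no basis in X.d.** The FJS is a score with no pass mark there, and the 96% comes from another study. The documents do not support saying that the trial would report 96% against a true 88% to 93%.

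**A separate SAP or VII.H may settle it.** X.e announces a SAP, but already states the missing-data and six-month rules itself. VII.H includes early discontinuers only where appropriate, which does not override X.e.

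**Conclusion.** The concern holds for the patient half of the success endpoint. Followed as written, VIII.F.2 and X.e remove never-implanted ORIGIN patients and patients in either arm who are re-operated within six months, so these events cannot lower success there. A 3D-planning failure escapes the surgeon half as well. This is more than a missing definition, because stated rules produce the bias. It is confined to the success endpoint.

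The size is unknown. The fall from 96% to about 93% to 88% rests on a borrowed satisfaction figure and on an assumed 2 to 5 removals among 63 patients. It shows only that a few events would matter.

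**What to change.** In X.d, define device/procedure success by arm for all randomised patients, and state the following:

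- In either arm, non-implantation of the allocated device for device, planning or procedural reasons counts as a failure and not as missing. This includes every attempted procedure under VIII.F.2, with the same recording for VANGUARD.
- Revision or further surgery on the study knee that is related to the original procedure, up to the visit concerned, counts as a failure.
- The six-month exclusion in X.e does not apply to this endpoint.
- Satisfaction is reported as a separate component.
- Withdrawals, cancellations unrelated to the device, and losses without known failure are shown separately and are not counted as device failures.

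Then reconcile VII.H (subject withdrawal), VIII.F.2, X.c, X.d and X.e, so that each says which patients enter which analysis.

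The cost is wording and one derived variable. ORIGIN attempts and re-operations in both arms are already recorded; equivalent recording of non-implantation for VANGUARD has to be added. The downside is that the reported success rate may be slightly less favourable.

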### e) *Statistical Methods and Analysis*

All analyses will be described in a Statistical Analysis Plan (SAP) which will be completed prior to analysis. No interim analysis is planned.

Any deviations from this section and/or the Statistical Analysis Plan will be described and justified in the Final Clinical Study Report, as appropriate.

No statistical techniques will be used to impute missing data for continuous or categorical outcomes. If a subject's data are missing for any reason, that subject will not be included in that portion of the analysis. The number of subjects included in each analysis will be reported so that the reader can assess the potential impact of missing data.

Additional (annual) reports providing only descriptive statistics will only be written upon request of the EC/IRB and/or Regulatory Authority, as applicable.

For statistical analysis, patient satisfaction results will be analyzed into the knee awareness as:

- Never
- Almost never
- Seldom
- Sometimes
- Mostly

The subjects that required further procedures or surgeries on their knee in the initial six months were excluded from this analysis. These patients were excluded from analysis because the outcome and satisfaction scores were likely to be highly influenced by the early additional procedure, and the study was not powered to evaluate the revision rates associated with two implants.

Statistical differences could be identified in:

- Baseline demographics between ORIGIN vs VANGUARD in patient satisfaction, including slightly differences in age, comorbidities and sex.
- Surgeon overall satisfaction regarding both implants ORIGIN and VANGUARD and possible surgical factors who could play a role in the patient outcome or on the performance of the implant?
- Demonstrate superiority of ORIGIN over VANGUARD: higher score by 13.4 points based on MCID evaluation of PROMs.
- If a modular stem is used it could impact radiological analysis: radiolucencies for instance and tibial loosening

SYMBIOS		 symbios  Clinical Investigation Plan	F029.03
Date	27.11.2019		Distribution Informatique pdf
Auteur	BGA		
Contrôle	EBO		
Libération	RAQ		

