All subjects will be encouraged to remain in the study through the last follow-up visit at two years. Subjects who discontinue participation prematurely will be included in the analysis of results (as appropriate) but they will not be replaced in the enrollment of total study subjects. If a study subject is discontinued from the study early, the reason for discontinuation should be documented in the subject file and a Study Exit e-CRF must be completed. If discontinuation is because of safety or lack of effectiveness, the patient shall be asked to be followed for collecting safety data outside the clinical study.

Once a subject has been enrolled in the study (i.e. written Informed Consent has been obtained) he/she may withdraw his/her consent to participate in the study at any time without prejudice. Participation in this study is entirely voluntary.

If a subject discontinues the study at any time, is withdrawn from the study early, or completes all follow-up visits they should continue to be followed by the implanting center according to their standard clinical practice.

SYMBIOS		 symbios  Clinical Investigation Plan	F029.03
Date	27.11.2019		Distribution Informatique pdf
Auteur	BGA		
Contrôle	EBO		
Libération	RAQ		

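### Section X.e omits patients with missing data and plans no sensitivity analysis; two removals follow randomisation, no primary analysis set is defined, and pre-operative FJS is not assigned to the 1-year comparison

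*Combined protocol and SAP*

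**What the plan says.** Section X.e sets the missing-data rule itself: "No statistical techniques will be used to impute missing data for continuous or categorical outcomes". Where a subject's "data are missing for any reason, that subject will not be included in that portion of the analysis". The safeguard is disclosure: "The number of subjects included in each analysis will be reported so that the reader can assess the potential impact of missing data". The analyses are otherwise left to a later SAP, but "Any deviations from this section and/or the Statistical Analysis Plan will be described and justified in the Final Clinical Study Report".

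Four places bear on who is analysed:

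- **Section X.e**: "The subjects that required further procedures or surgeries on their knee in the initial six months were excluded from this analysis". The sentence follows a list of knee-awareness categories, so it is unclear whether it removes patients from the 1-year FJS comparison or only from that categorical summary.
- **Section VIII.F, Attempted procedure**: a patient randomised to ORIGIN who is not implanted, including for shape incompatibility found at 3D planning, stays only briefly: "the subject will be followed for safety reporting for 30 days post-attempted implant, and then exited from the study". No counterpart is given for VANGUARD.
- **Section VII.H.c**: people who discontinue early are analysed so far as appropriate.
- **Section X.c**, on clinical data and safety outcomes: all enrolled patients are analysed.

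Pre-operative FJS is collected (Section VIII.F.a; schedule in XXI.B). The primary endpoint is a between-arm comparison at 1 year (Synopsis; Section VI.B). The only stated use of pre-operative values, at the end of VI.B, is improvement to two years.

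**The concern.** The trial is unblinded (Section VII.C) and the primary outcome is patient-reported, so patients who know their implant could be lost at different rates, or for different reasons, in the two arms. Section VIII.H itself lists loss above 10% as a threat to interpretation. The number analysed shows how many are missing. It does not show which way the result may have moved.

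The two removals raise a related problem. Patients are randomised about 6 to 8 weeks before surgery (Section VII.I), and the planning CT is done only for those assigned to ORIGIN. An anatomy found unsuitable at planning therefore leaves the ORIGIN arm, while the same anatomy in the VANGUARD arm stays. The six-month exclusion depends on an event after surgery. Randomisation protects neither comparison, and without a defined primary analysis set the text does not say whether either removal applies to the FJS result.

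**Working it through.** **Inputs from the protocol (Section X.a–b).** SD 26.8; difference 13.4; two-sided alpha 0.05; power 80%; 10% loss; 70 per arm.

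**The plan's own figure.** n = (2/0.5²) × (1.96 + 0.84)² = 8 × 7.84 = 62.72, so 63; 63/0.90 = 70. Both reproduce. Power at 63 per arm is 80.1% by the normal formula and 79.5% by the t-test used below.

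**Bias of the available-case rule.** Let p be the share lost in an arm and g the mean of those kept minus the mean of those lost, with higher scores better. The observed mean exceeds the full-arm mean by p × g, so the contrast is biased by p₁g₁ − p₂g₂. This is zero if g is zero in both arms, or if the two terms are equal.

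**Scenarios.** The loss splits and gaps are assumptions; the protocol gives neither. With the same gap in both arms, |bias| = g × |p₁ − p₂|. SE = 26.8 × √(1/n₁ + 1/n₂) with n = 70(1 − p), about 4.78 in each row. Type I error = Φ(−1.96 + b/SE) + Φ(−1.96 − b/SE). Power is by noncentral t, with a true difference of 13.4 and the bias running against ORIGIN.

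| Loss by arm | Bias, g = 10 / 20 / 30 | Type I error, % | Power at g = 20 |
|---|---|---|---|
| 10% v 10% | 0 / 0 / 0 | 5.0 / 5.0 / 5.0 | 79.5% |
| 9% v 11% | 0.2 / 0.4 / 0.6 | 5.0 / 5.1 / 5.2 | 77.1% |
| 8% v 12% | 0.4 / 0.8 / 1.2 | 5.1 / 5.3 / 5.7 | 74.5% |
| 5% v 15% | 1.0 / 2.0 / 3.0 | 5.5 / 7.0 / 9.6 | 65.7% |

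Equal loss with unequal gaps also biases: 10% in each arm with gaps of 20 and 10 gives 0.10 × 20 − 0.10 × 10 = 1.0 point.

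**ORIGIN-only exits.** With k of 70 exited, the shift is g × k/70. For k = 1, 3 and 7 (assumed) it is 0.1, 0.4 and 1.0 points at g = 10, and 0.3, 0.9 and 2.0 at g = 20. It is zero if these patients would have scored like the rest.

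**Six-month exclusion.** Section IV.B reports, for ORIGIN at mean 1.0 year, complications with revision in 0.25% and without in 3.25%. In 70 patients that is 0.0025 × 70 = 0.2 and 0.0325 × 70 = 2.3. Not every complication is a further procedure, so about 0 to 2 exclusions per arm is a fair guess. Two at a gap of 30 shift an arm by 30 × 2/70 = 0.9 points. The registry rate in the same section, 5.3% of 19, is one patient. It would give 3.7 per 70, or 20 × 3.7/70 = 1.1 points at a gap of 20, but one event is too little to plan on.

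**What a sensitivity analysis could decide.** At 63 per arm, significance needs an observed difference of 1.979 × 4.775 = 9.45 points. With 7 of 70 missing in one arm, worse-score shifts of 10, 20 and 30 move the contrast by 1, 2 and 3 points. Results between about 9.5 and 12.5 are the ones at risk if success means p < 0.05.

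**Baseline adjustment.** The effect becomes 0.5/√(1 − r²). At 63 per arm, power goes from 79.5% to 81.1% (r = 0.2) or 83.1% (r = 0.3); r is assumed.

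**The case against.** Several points on the other side are sound.

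- **A reader might infer that unequal loss alone biases the result.** It does not: if those lost resemble those kept, the bias is zero, and terms from the two arms can offset.
- **The assumed gaps are large.** Gaps of 20 to 30 points exceed the 13.4-point MCID, and nothing in the protocol supports them. Near the planned loss the effect is small even so.
- **A reader might infer a four-way contradiction on who is analysed.** The text does not support that. Section VII.H.c is compatible with an available-case rule, X.c may concern safety only, and the attempted-procedure rule governs follow-up rather than an analysis set. What stands is an undefined primary set and two removals after randomisation.
- **The SAP is still to come.** It may name the model, covariates, analysis sets and evaluability criteria, so the absence of criteria in Section XI.c is not counted here. The answer is weaker for imputation: X.e fixes that rule, and a SAP that imputed would be a departure to describe and justify.
- **Other protections exist.** Contact attempts, documented reasons for discontinuation and the 10% allowance all help. None shows how the FJS result depends on those missing.
- **An unadjusted randomised comparison is valid.** True; baseline adjustment adds precision only and does not cure dropout bias.
- **Success may mean 13.4 points rather than p < 0.05.** Section X.e speaks of a "higher score by 13.4 points based on MCID evaluation of PROMs". On that reading the range at risk moves to about 13.4 to 16.4 points (13.4 + 3), but the need for the analysis remains.

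**Conclusion.** The point holds as a gap worth closing, not as evidence that the trial would be seriously biased. Under assumed gaps of 10 to 30 points, available-case bias is 0.2 to 1.2 points near the planned 10% loss (type I error 5.0–5.7%). It becomes material only with marked imbalance: 1 to 3 points at 5% v 15% (5.5–9.6%). The six-month exclusion is probably worth under 1 point, judging by ORIGIN-only rates; no VANGUARD rate is given. The size of the ORIGIN-only exits depends on a failure rate that the protocol does not state. Confidence is medium, because loss patterns, gaps and the baseline correlation are assumptions and the SAP is not available. The change is still advisable: it is cheap, and the no-imputation rule sits in the protocol itself.

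**What to change.** In Section X.e:

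1. **Primary comparison.** Compare 1-year FJS by randomised arm in all randomised patients with a 1-year FJS, including those with early further procedures. Make the six-month exclusion a sensitivity analysis only.
2. **Baseline.** Adjust for pre-operative FJS (ANCOVA) and report the unadjusted result beside it.
3. **Missing data.** Keep the primary analysis free of imputation and report numbers missing by arm with reasons. Permit one sensitivity analysis: multiple imputation in all randomised patients whose data may be used (Section XV gives a right of erasure), counting the attempted-procedure exits as missing. Apply worse-score shifts of 0, 10, 20 and 30 points, varied separately by arm, and report the shift at which the conclusion changes.
4. **Reconcile first.** Settle the FJS direction, since a worse score is otherwise undefined: Section VIII.F.e makes low scores best, while IV.B grades a mean of 12.9 as poor and X.e expects a higher score with ORIGIN. Reconcile the closing sentence of VI.B, on improvement to two years, with the 1-year between-arm comparison.

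The cost is protocol wording with ethics review (Section XIII), SAP text and some programming. Pre-operative and 1-year FJS are already collected. Patients without a pre-operative FJS drop out of the adjusted model, hence the unadjusted result beside it, and the imputation rests on assumptions, which the shifts vary.
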